#### **4.4.6. Change from baseline of CGI-CSID**

The CGI-CSID is from the 7-point Caregiver Global Impression of Change in Seizure Intensity/Duration instrument. The scores range from 1=very much improved and 7=very much worse. The number and percentage of subjects with each score will be

summarized. The baseline and post-baseline values and the arithmetic changes from baseline will be summarized using descriptive statistics.

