## 4 STUDY DESIGN

### 4.1 Overall Design

This is a Phase 3, global, OLE study of adjunctive GNX treatment in children and adults with TSC-related epilepsy who previously participated in either Study 1042-TSC-3001 or Study 1042-TSC-2001. For this protocol, the term children will refer to the full range of pediatric participants.

For all participants who enter the OLE, the last visit in the parent Study 1042-TSC-3001 or Study 1042-TSC-2001 will be the same as the First Visit in this OLE study and visit activities will not be duplicated.

Procedures specific to this protocol and not otherwise considered standard of care, will not be performed until written informed consent/assent from the participant or their parent(s)/LAR(s), as appropriate, has been appropriately obtained.

Participants or their parent(s)/caregiver(s)/LAR(s) are expected to complete electronic seizure diary (eDiary) entries to document the number and type(s) of seizures daily throughout the first year of the study. After the first year, study assessments will focus on safety evaluation.

Caregiver and clinician global impressions of improvement will continue to be assessed to ensure that participants are continuing to receive benefit from treatment. A variety of clinician and caregiver administered outcome measures will be used at the study visits to assess efficacy. These include:

- Clinical Global Impression of Improvement (CGI-I) by parent(s)/caregiver(s) and clinician.
- Caregiver Global Impression of Change in Seizure Intensity/Duration (CGI-CSID).

- Short Form 36 (SF-36) (first year of the study only).

Safety monitoring assessments will be conducted throughout the study.

The maximum dose for all participants is 1800 mg/day.

Participants who discontinue the investigational product (IP) should undergo a 2-week taper period. The taper period may be shortened, if necessary, for participant safety. Participants who discontinue the IP before the scheduled completion of the study will have an Early Termination Visit, as per Visit 13 (Week 156), and return to the site 2 weeks after the end of the taper period to complete the safety follow-up assessments.

The study design is presented in Figure 1.

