### **8.2.3 Caregiver Global Impression of Change in Seizure Intensity/Duration**

The CGI-CSID is a 7-point Likert scale in which the parent(s)/caregiver(s)/LAR(s) assesses change in seizure intensity and/or duration after initiation of investigational product relative to baseline (prior to treatment with investigational product). The scale ranges from 1- very much improved, 2- much improved, 3- minimally improved, 4- no change, 5- minimally worse, 6- much worse, and 7- very much worse (Section 10.9).

CGI-CSID will be assessed at Visit 1 (First Visit of the OLE), Visit 3 (Week 26), Visit 5 (Week 52), Visit 7 (Week 78), Visit 9 (Week 104), Visit 11 (Week 130), and Visit 13 (Week 156).

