### **2.3.2. Secondary Endpoints**

The secondary endpoints are:

- Percentage change from baseline in 28-day seizure frequency during open-label treatment (first year only)
- Number (%) of participants considered treatment responders (first year only)
- CGI-I at the last scheduled study visit
- Change from baseline in the quality-of-life scale SF-36 (first year only)
- Change from baseline in the percentage of seizure-free days during treatment, based on seizure type (first year only)
- Change from baseline of CGI-CSID

Note that original baseline in 28-day seizure frequency in the parent study will be applied. For other assessments, the baseline is considered to be Visit 1, the first visit of the OLE.

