### 5.2. Analysis Visit Windows

#### Efficacy Analyses

Efficacy analyses will use data only from scheduled visits. Data will be reported by designated visit. Data collected at unscheduled visits will be provided in listings. For analysis of data collected across specific study periods, the following definitions will be applied:

- Baseline for efficacy assessments is defined as based on the participant's prior study as follows:
  - Study 1042-TSC-2001 – the original 4-week screening period for participants continuing in Study 1042 TSC-3002
  - Study 1042-TSC-3001 – the original 4-week screening period for participants previously randomized to GNX.
- 3-year open-label treatment period: Visit 2 to Visit 13. All windows for these visits are  $\pm$  14 days.

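### The CGI-CSID change from baseline subtracts one rating of change from another, so a rating that stays the same scores 0 whatever the benefit

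*SAP*

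**What the plan says.** **The scale.** In Protocol 8.2.3 the caregiver "assesses change in seizure intensity and/or duration after initiation of investigational product relative to baseline (prior to treatment with investigational product"). The seven categories are "1- very much improved, 2- much improved, 3- minimally improved, 4- no change, 5- minimally worse, 6- much worse, and 7- very much worse". The first OLE rating is at Visit 1. Ratings follow at Visits 3, 5, 7, 9, 11 and 13.

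**The endpoint.** Protocol Section 3 and SAP 2.3.2 both list change from baseline of the CGI-CSID as a secondary endpoint. In the protocol it does not carry the footnote mark that points to the parent-study baseline.

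**The baseline.** SAP 2.3.2 applies the parent-study baseline to 28-day seizure frequency and then states: "For other assessments, the baseline is considered to be Visit 1, the first visit of the OLE". The note under the protocol's endpoint table says the same. SAP 5.2, under Efficacy Analyses, has competing wording: "Baseline for efficacy assessments is defined as based on the participant's prior study as follows", followed by the parent study's 4-week screening period. SAP 4.4.1 repeats that definition. SAP 4.4.6 names no baseline visit of its own.

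**The state at Visit 1.** Protocol 4.1 says the last parent-study visit "will be the same as the First Visit in this OLE study and visit activities will not be duplicated". The synopsis, under Intervention Groups and Duration, adds that participants randomised to placebo in Study 1042-TSC-3001 are titrated to ganaxolone before that study ends.

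**The analysis.** SAP 4.4.6 has two parts. One is a frequency table: "The number and percentage of subjects with each score will be" summarised. The other is the subtraction: "The baseline and post-baseline values and the arithmetic changes from baseline will be summarized using descriptive statistics".

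**The concern.** Subtracting a baseline makes sense when both values are absolute measurements on one scale, such as the percentage of seizure-free days in SAP 4.4.5. The CGI-CSID is not of that kind. The rater has already made the comparison with the pre-treatment state, and the score is the result. Taking the Visit 1 score away removes whatever improvement or worsening had been reached by OLE entry. What remains is movement in the caregiver's impression since Visit 1, and the SAP does not label it so.

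The result would be reported under the endpoint's own name. Someone reading a mean change near 0 would naturally take it to mean no change in seizure intensity or duration on ganaxolone. The figure cannot say that: maintained benefit, no benefit and maintained harm all give the same value, and in some cases the sign runs opposite to the participant's standing against pre-treatment.

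**Working it through.** The plan states no numerical target for this endpoint, so there is no figure to reproduce. The check applies the SAP's rule to possible scores.

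**Inputs**
- Score range 1 to 7, with 4 = no change from pre-treatment (Protocol 8.2.3).
- Baseline = OLE Visit 1 (SAP 2.3.2; note to the endpoint table in Protocol Section 3).
- Planned change = later score − Visit 1 score (SAP 4.4.6).
- Comparison: later score − 4, the standing against pre-treatment that the scale itself defines. Negative is better.

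| Visit 1 → later | Planned change | Later score − 4 |
|---|---|---|
| 1 → 1 | 1 − 1 = 0 | −3 |
| 2 → 2 | 2 − 2 = 0 | −2 |
| 3 → 3 | 3 − 3 = 0 | −1 |
| 4 → 4 | 4 − 4 = 0 | 0 |
| 6 → 6 | 6 − 6 = 0 | +2 |
| 2 → 3 | 3 − 2 = +1 | −1 |
| 7 → 5 | 5 − 7 = −2 | +1 |
| 4 → 2 | 2 − 4 = −2 | −2 |

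The first five rows are five different clinical standings with one planned value. In the 2 → 3 row the planned change reads as worsening for someone still improved over pre-treatment. In the 7 → 5 row it reads as improvement for someone still worse. Only when Visit 1 is 4 do the two columns agree by construction, as in the rows 4 → 4 and 4 → 2.

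**Group illustration.** Assume that a share r is rated 2 at every visit and the rest are rated 4 at every visit. These shares are assumptions; the documents give no CGI-CSID data.
- Mean planned change = r × 0 + (1 − r) × 0 = 0 for every r.
- Mean score = 2r + 4(1 − r) = 4 − 2r.
- r = 20%: 4 − 0.40 = 3.60.
- r = 30.4%: 4 − 0.608 = 3.39. The share is borrowed from the Phase 2 proportion with at least a 50% seizure reduction, which is a different measure and serves only as a value for r.
- r = 50%: 4 − 1.00 = 3.00.
- r = 100%: 4 − 2.00 = 2.00.

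The mean score moves from 3.60 to 2.00 while the planned mean change stays at 0.

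**Does the competing baseline help?** If SAP 5.2 and 4.4.1 governed, baseline would be the parent-study screening period. A rating of change since the product was started cannot exist before it was started. That reading therefore supplies no score to subtract.

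**How the SAP treats the sister scale.** The CGI-I also has seven points and a pre-treatment reference (Protocol 8.2.2). Its endpoint is the score itself, and SAP 4.4.3 tabulates only the number and percentage at each score. No reason is given for treating the CGI-CSID differently. The closing sentence of SAP 4.4.6 is identical to that of 4.4.5, where subtraction is valid, so it may have been carried over.

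**The case against.** The strongest reply is that most of what is needed is already planned. SAP 4.4.6 tabulates every raw score, and SAP 5.2 has efficacy data reported by designated visit. A participant rated 2 throughout will appear as much improved each time, and the percentages rated 1–2 or 1–3 are sums of table rows. This stands: a reader might infer that the analysis hides the benefit of treatment, and the documents do not support that.

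A second reply is that movement since OLE entry is a fair question in a long-term extension, and that 0 is then the right answer for maintained benefit. This stands in part. It also answers a charge that the endpoint is biased toward no effect: bias needs a stated target, and SAP 3.2 makes every endpoint descriptive. But the SAP does not say that movement since entry is the target, and the difference alone cannot separate maintained benefit from maintained absence of benefit.

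Two further inferences are tempting and should not be drawn.
- **That the result depends on parent-study arm rather than current benefit.** The difference depends on the current score and the Visit 1 score. Visit 1 scores might differ by arm through length of ganaxolone exposure, but the documents give no such scores, and SAP 4.1 summarises results by parent-study treatment.
- **That a participant rated 1 at Visit 1 cannot improve because of the subtraction.** That is the end of a 7-point scale, and the raw score has the same limit.

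Finally, the endpoint name comes from the protocol, so the SAP is implementing what it was given. That is true, and it affects how the change must be documented.

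**Conclusion.** The point holds, confined to the change-from-baseline summary in SAP 4.4.6. Under the documents' own definitions the named secondary endpoint is a difference of two change ratings. It is 0 for any participant whose rating is the same at Visit 1 and later, whatever that rating is, and its sign can disagree with the participant's standing against pre-treatment.

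The conclusion rests on Visit 1 being the baseline for this scale. That is what SAP 2.3.2 and the protocol note say, and the alternative wording in SAP 4.4.1 and 5.2 cannot yield a score. The zero applies to participants with an unchanged CGI-CSID rating, not to responders defined by seizure frequency. Participants still changing after Visit 1, possibly including some who came from placebo, would have non-zero differences. How often each pattern will occur cannot be known from the documents.

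The raw score table is kept. No hypothesis test, error rate, power or sample size is affected, and neither is the primary safety objective. The change is worth making because a named secondary endpoint would otherwise be reported by a figure that does not mean what its name suggests.

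**What to change.** 1. In SAP 4.4.6, make the CGI-CSID score at each scheduled visit the reported endpoint: number and percentage at each score, with the percentages rated 1–2 and 1–3. This follows SAP 4.4.3 for the CGI-I.
2. Drop the arithmetic change. If movement since OLE entry is wanted, replace it with a shift table of Visit 1 score by later-visit score, labelled as movement since OLE entry.
3. Reconcile SAP 2.3.2 with 4.4.1 and 5.2 for this scale. State that the score's reference is the pre-treatment state and that Visit 1 is only the first OLE rating.
4. Record the departure from the protocol's endpoint name in SAP Section 6, which now reports no changes. If the SAP is already final, that section calls for an SAP amendment before database lock.

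The cost is a documented change to a secondary endpoint named in the protocol, and one table replaced. No new data are needed, because the ratings are already scheduled.

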#### **4.5. Handling of Missing Data**

Available data from patients who withdraw from the study prematurely will be included in analyses, unless otherwise indicated. Summary statistics will be reported based upon observed data. No data will be imputed or carried forward for missing values or for patients who discontinue early. All missing data and missing or partial dates for AEs and medications will be queried for a value. In the unlikely event that no value can be obtained, substitutions will be made as described below.

- Missing and Partial Start/Stop Dates - AEs and Concomitant Medications**

The handling of partial start and stop dates for AEs are described in

**Table 4** below. Similar algorithms for handling missing and partial dates of concomitant medication usage are described in **Table 5**. In both cases, if a stop date is complete and an imputed start date is after the stop date, the start date will be set to the stop date.

- **Missing Seizure/Medication Diary Entries**

The calculation of seizure frequency endpoints will include only days for which diary entries are available. Missing seizure data will not be imputed.

**Table 4: Adverse Event Start/Stop Date Imputation**

Parameter	Missing	Additional Conditions	Imputation
Start date for AEs	D	M and Y same as M and Y of first dose of IP	Date of first dose of IP
		Y same but M prior to month of first dose of IP	Last day of month
		Y same but M after month of first dose of IP	First day of month
		Y is prior to year of first dose of IP	Last day of month
		Y is after year of first dose of IP	First day of month
	M	Y is same as Y of first dose of IP	Month of first dose of IP
		Y is prior to year of first dose of IP	M = December
		Y is after Y of first dose of IP	M = January
	D and M	Y same as Y of first dose of IP	Date of first dose of treatment
		Y prior to Y of first dose of IP	M and D will be December 31
		Y after Y of first dose of IP	M and D will be January 1
Stop date for AEs	Y, or M, D, Y	Y and/or start date missing	Date of first dose of treatment
	D	M and Y not missing	Use last day of month (i.e. D may take on values of 28, 29, 30, or 31, depending on month)
		Y not missing; if D also missing, impute D as described above	M = December
	Y, or M, D, Y	Y and/or stop date missing.	No imputation. Date left missing.

D=day, M=month, Y=year

Note: In all cases, if an estimated start date is after a complete stop date, the start date will be set to the AE stop date. Similarly, if the estimated stop date is before a complete or imputed start date, use the last day of the start date month.

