### **8.4.1      Time Period and Frequency for Collecting Adverse Event and Serious Adverse Event Information**

All AEs are collected from the time of the first dose of the IP in the OLE until the defined follow-up period at the timepoints specified in the SOA (Section 1.3). Any AE that begins in a parent study and is ongoing at the time of the first dose of IP in the OLE will be included as an AE in the OLE. This includes events occurring during the initial visit in the study, regardless of whether or not the IP has been administered. All AEs reported after the initiation of IP will be considered treatment-emergent AEs. Where possible, a diagnosis rather than a list of symptoms should be recorded. If a diagnosis has not been made, then each symptom should be listed

individually. All AEs should be captured on the appropriate AE pages in the eCRF and in source documents. In addition to untoward AEs, unexpected benefits outside the IP indication should also be captured on the AE eCRF page.

Medical occurrences that begin before the start of study intervention but after obtaining informed consent will be recorded as medical history/current medical conditions, not as AEs.

All AEs must be followed to closure (the participant's health has returned to baseline status or all variables have returned to normal), regardless of whether the participant is still participating in the study. Closure indicates that an outcome is reached, stabilization is achieved (the investigator does not expect any further improvement or worsening of the event), or the event is otherwise explained. When appropriate, medical tests and examinations are performed so that resolution of event(s) can be documented.

All SAEs (regardless of relationship to study) are collected from the time the participant/parent(s)/LAR(s) signs the informed consent/assent until the defined follow-up period stated and must be reported to Marinus' drug safety vendor within 24 hours of the first awareness of the event.

In addition, any SAE considered "related" to the IP and discovered by the investigator at any interval after the study has completed must be reported to Marinus' drug safety vendor within 24 hours of the first awareness of the event.

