### 4.3. Statistical Methods for Primary Safety Analyses

#### 4.3.1. Adverse Events

Adverse events (AEs) are collected from the time of informed consent/assent through the defined follow-up period. AEs are coded using MedDRA dictionary, version 24.0 and are

categorized by system organ class (SOC) and preferred term (PT). A treatment-emergent AE (TEAE) is defined as an AE that starts or worsens on or after the first day of dosing with IP. Detailed by-patient listings of all AEs reported during the study will be provided and will include verbatim and coded terms for each AE.

For the safety Analysis Set, the following tabular summaries will be created:

- An overall summary of TEAEs will present the number and percentage of subjects with at least 1 reported TEAE, study drug related TEAE, serious TEAE, TEAE of Grade 3 or higher, study drug infusion interruption, and death
- TEAEs by system organ class and preferred term
- TEAEs by system organ class, preferred term, and maximum severity
- Study drug related TEAEs by system organ class and preferred term
- TEAEs by decreasing frequency of preferred term
- Moderate or severe TEAEs by system organ class and preferred term
- Moderate or severe study drug related TEAEs by system organ class and preferred term
- TEAEs that led to study drug infusion interruption by system organ class and preferred term
- Serious TEAEs by system organ class and preferred term
- Serious study drug related TEAEs by system organ class and preferred term

For incidence reporting, if a subject reported more than 1 AE that was coded to the same preferred term/system organ class, the subject will be counted only once for that specific preferred term/system organ class. For TEAEs presented by severity, the worst severity for each event during the clinical trial will be presented for each subject. If the severity is missing for a TEAE, then a severity of “Severe” will be assigned. The imputed values for severity assessment will be used for incidence summaries, while the actual values will be used in data listings.

For TEAEs presented by relationship to study drug, the closest relationship to study drug for each event during the clinical trial will be presented for each subject. If the relationship to investigational product is missing for a TEAE, a causality of “Related” will be assigned. The imputed values for relationship assessment will be used for incidence summaries, while the actual values will be presented in data listings.

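### SAP Table 4 can date an adverse event (AE) before first dose when only its start month is missing, dropping it from the TEAE tables; with less date information it would be kept

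*SAP*

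**What the plan says.** SAP Section 4.5 first queries missing and partial AE dates and imputes only if no value can be obtained. Table 4 then treats the start date separately according to which part is missing. Where the AE falls in the first-dose year:

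- **Day missing, same month as first dose:** "Date of first dose of IP".
- **Month missing** (condition "Y is same as Y of first dose of IP"): the "month of first dose of IP" is inserted. The recorded day is left as it is.
- **Day and month missing:** "Date of first dose of treatment".

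The only correction to an imputed start date is against the stop date: "if an estimated start date is after a complete stop date, the start date will be set to the AE stop date". No rule prevents an ambiguous start from falling before first dose.

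SAP Section 4.3.1 gives the definition that decides which events are tabulated: "A treatment-emergent AE (TEAE) is defined as an AE that starts or worsens on or after the first day of dosing with IP". Its tabular AE summaries are built on TEAEs. Protocol Section 8.4.1 says "All AEs are collected from the time of the first dose of the IP in the OLE". It also brings in AEs that began in a parent study and are still ongoing at that dose, and it treats AEs reported after the start of IP as treatment-emergent.

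**The concern.** The month-only row is the odd one out. In the other start-date rows, a date that is ambiguous relative to first dose resolves to the first-dose date. A pre-dose date is assigned only when the known month or year proves it. The month-only row can turn an ambiguous record into a pre-dose one, so an AE with a known day can be lost when the same AE with no day would be kept. This also runs against the SAP's cautious defaults in Section 4.3.1, where missing severity is taken as severe and missing causality as related.

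At stake is AE incidence, the first-listed primary endpoint in a study whose primary objective is long-term safety. An AE first reported in the extension is presumptively on treatment under Protocol Section 8.4.1, yet this row can remove it from the summaries.

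**Working it through.** **Inputs.** The rule and its only correction come from SAP Table 4; the TEAE definition comes from SAP Section 4.3.1. First dose of IP is read as the first extension dose. The documents state no figure to reproduce and no rate of month-only gaps.

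**Condition for the error.** Let first dose be on day f of month m, and let the recorded AE day be d in the same year. The imputed start is day d of month m, which is before first dose exactly when d < f.

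**Example.** First dose is 20 June 2023; the AE is recorded as day 10, month unknown, 2023.
- Imputed start: 10 June, 10 days before dosing, so not a TEAE.
- Same-year dates on or after first dose that fit the record: the 10th of July to December, six dates, all on treatment.
- With the day also missing: 20 June, a TEAE.

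**Share affected for a given first-dose date.** Assume onset is uniform over the days from first dose to 31 December. The wrongly dated onsets are days 1 to f − 1 of each later month, so for the dates below the count is (12 − m)(f − 1). The calendar year 2023 is illustrative.

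| First dose | Days left in year | Dated pre-dose | Share |
|---|---|---|---|
| 5 March | 302 | 9 × 4 = 36 | 11.9% |
| 15 March | 292 | 9 × 14 = 126 | 43.2% |
| 25 March | 282 | 9 × 24 = 216 | 76.6% |
| 5 June | 210 | 6 × 4 = 24 | 11.4% |
| 15 June | 200 | 6 × 14 = 84 | 42.0% |
| 25 June | 190 | 6 × 24 = 144 | 75.8% |
| 15 September | 108 | 3 × 14 = 42 | 38.9% |
| 15 December | 17 | 0 × 14 = 0 | 0% |

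**Average over all first-dose dates in the year.**
- Pairs with onset on or after first dose: 365 × 366 / 2 = 66,795.
- Pairs dated pre-dose: for each month, 12 − m times the sum of (f − 1) over its days. That sum is 465 for a 31-day month, 435 for a 30-day month and 378 for February. The total is 29,280. Subtract 3 for late-January first doses, because 29 and 30 February do not exist. This leaves 29,277.
- Share: 29,277 / 66,795 = 43.8%.
- Impossible dates (for example day 31 put into a 30-day month): by first-dose month February, April, June, September and November, 728 + 150 + 120 + 60 + 30 = 1,088, and 1,088 / 66,795 = 1.6%. Table 4 has no rule for these.

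**Opposite direction.** First dose is 20 November; a parent-study AE truly began on 25 August and is still ongoing, recorded as day 25, month unknown. The imputed start is 25 November, so an AE with pre-dose onset becomes a TEAE.

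**With the amended row (see fix).** None of the 66,795 on-treatment pairs is dated before first dose.

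**The case against.** **The records will be rare.** A known day and year with no month is unusual, the row applies only in the first-dose year, and a query must fail first. The study is descriptive, so no decision rule depends on the count. The AEs stay in the listings, and one recorded as worsening on treatment is still a TEAE. All of this stands. It limits the size of the problem but does not make the row correct.

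**The row does not only remove events.** A reader might infer a purely downward bias. The documents do not support that: every participant rolls over from a parent study, Protocol Section 8.4.1 carries ongoing parent AEs into the extension, and the November example shows one moved to after first dose. Understatement can be claimed only for AEs newly reported in the extension.

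**Not every affected AE is probably on treatment.** Ignoring when AEs are collected, and with first doses spread evenly over months, the share of candidate months on treatment for an affected record averages 5.5 / 12 = 46%. For day 15, it is 10 of 12 months with first dose on 20 February, 5 of 12 for 20 July, 2 of 12 for 20 October and none for 20 December. The presumption comes from the protocol's collection window. SAP Section 4.3.1 instead starts collection at consent, and the protocol includes events at the initial visit even before IP is given.

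**Roughly half is not the loss rate.** Two independent days drawn uniformly from 1 to 28 give P(d < f) = 27/56 = 48%, but this also counts AEs correctly placed before dosing. Restricted to on-treatment onsets, the figure is 43.8%.

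**Conclusion.** The point holds as a minor defect: the month-only row, as written, can misclassify an ambiguous AE that the neighbouring rows would keep as a TEAE. For AEs newly reported in the extension, it understates TEAE incidence. For carried-over AEs, the direction is not determined.

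The 43.8% (about 11% to 77% for first doses from the 5th to the 25th in March or June, and 0% in December) is a share of on-treatment, same-year AEs with only the month missing, under uniform first-dose and onset dates. It is not a share of all AEs. The number of AEs lost cannot be estimated from the documents and should be very small. For a December first dose, a pre-dose result is correct, because no later month remains in that year.

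**What to change.** Amend the Table 4 row for a missing month in the first-dose year to read: use the month of first dose; if the resulting date is before the first dose of IP or is not a valid date, use the date of first dose, unless the known information shows onset before first dose. That exception covers three cases:

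- no date with that day in that year falls on or after first dose (for example, some records with a December first dose);
- a complete stop date lies before first dose;
- an earlier start is documented in the parent study.

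The first exception is needed. Without it, a day-15 AE with first dose on 20 December would become a TEAE although all 12 possible dates precede dosing.

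The cost is one clause and one programming condition, made by SAP amendment before database lock as SAP Section 6 provides. The downside is that a few AEs with true pre-dose onset and unknown month may be counted as TEAEs, the same cautious direction as the neighbouring rows. The change does not by itself correct carried-over AEs whose inserted date already falls after first dose.
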